Research Blood Draw (mL)	NA	66	10	10	10	66	66	NA
Visit Draw Total (mL)	NA	66	10	10	10	66	66	NA
General Assessments								
Demographics						X	X	
Concomitant Medications			X	X	X	X	X	X
Physical Exam ²⁹			X	X	X	X	X	X
Vital Signs including heart rate & sitting systolic/diastolic blood pressure				X				X
Vital Signs including heart rate, sitting systolic/diastolic blood pressure, weight, & waist circumference						X	X	
AE/SAE Assessment			X ³⁰	X ³⁰	X ³⁰	X ³⁰		X ³⁰
Profile 29 v2.0			X			X		X
Epidemiologic Questionnaire				X ³¹		X ³¹	X	
Dietary Assessment Questionnaire						X ³¹	X	
Self-Reported Joint Symptoms, including modified MDHAQ			X	X	X	X	X	X
Evaluate family member participation ³²			X	X	X	X	X	X
Pregnancy Status Check				X ³¹	X ³¹	X ³¹	X ³¹	X ³¹
Follow-up Telephone Assessments ³³		X ³¹						
Annual Phone Call for Withdrawn Subjects					X ³⁴		X ³⁴	
Disease Status								
Joint Examination – Physician’s Assessment: 64 /66 tender/swollen joint count ³⁵				X ³⁶	X ³⁶	X ³⁶	X	X ³⁶
Real Time Core Outcome Testing (hsCRP, IgM-RF, Anti-CCP3) & serum ³⁷			X ³⁸				X ³⁹	
Future Core Outcome Testing (hsCRP, IgM-RF, Anti-CCP3) & serum				X ³¹	X ³¹	X ³¹		X
2010 ACR/EULAR Criteria ⁴⁰			X					
X-ray as needed ⁴¹			X ⁴¹					
Clinical Laboratory Assessments								
Hematologies: Hemoglobin, Hematocrit, WBC (with differential), & Platelet count								X ⁴²
Chemistries: Serum creatinine, ALT, & AST								X ⁴²
STAT Urine Pregnancy Test			X ⁴¹					
Required Mechanistic Specimens ³¹								
PBMC/Plasma/DNA, RNA, Urine ⁴³			X ⁴⁴			X ³¹	X	
HCQ Level ⁴⁵						X ⁴⁶	X ⁴⁶	

²⁸ See protocol section 6.5.9, *Evaluations Triggered by a Swollen Joint*, for additional details.

²⁹ Physical Exam: Full PE at Screen, Week 52, Time of Diagnosis and Month 36/Early Termination. Symptom-driven PE at all other clinic visits.

³⁰ Non-serious adverse events will not be collected after Month 18. SAEs will be collected for the duration of the study.

³¹ These procedures will be conducted if the subject **has not** been previously diagnosed with clinically-apparent RA.

³² All participants should complete the “Participation of First Degree Relatives” questionnaire. If the subject consents to linking his/her information with a participating family members, please follow the Process for Linking First Degree Relatives in the Manual of Operations.

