7.3.2 Collection Period

AEs of NCI-CTCAE Grade 2 and above will be collected from the time the subject signs the main clinical trial informed consent until he/she initiates study intervention or until he/she is determined to be ineligible to receive study intervention, if the investigator determines that the AE is related to a study-mandated procedure, treatment, or change in treatment.

Regardless of whether the above is applicable, for all participants, AEs of NCI-CTCAE Grade 2 and above will be collected from the time of initiation of study intervention (i.e., the administration of the first dose of study drug (HCQ/placebo), as defined in Section 6.5.3, *Baseline/Randomization Visit*), until Month 18 or until 30 days after he/she prematurely withdraws (without withdrawing consent) or is withdrawn from the study.

Serious adverse events will be collected throughout the duration of the subject’s participation in the study.

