8.3.2 Safety Analysis

All safety analyses will be performed using the Safety Population.

The frequency of AEs will be summarized by system organ class, preferred term, severity (grade), and relationship to study treatment. Relationship to study treatment will be categorized as either treatment related (possibly, probably, or definitely related to study medication) or unrelated (unlikely related or unrelated). Similar analyses will be performed for SAEs. To account for differential duration of study participation among subjects, the summaries will also include the event rate (i.e. number of events per person-time) in addition to the number and percent of events and subjects experiencing events.

For each key safety endpoint defined in Section 3.3.2, *Secondary Safety Endpoints* the proportion of subjects experiencing at least one event in each treatment group will be reported and the treatment groups compared based on Fisher's Exact Test.

Laboratory parameters will be summarized both overall and by treatment group using appropriate descriptive statistics. For each lab parameter, the number and percent of subjects that have an increase, decrease, or no change from Baseline to Week 52, Month 24, and 36 will be displayed for each treatment group and pooled across treatment arms. For parameters with an explicit NCI-CTCAE grading criterion, change from baseline will be indicated by a change in grade. For parameters that do not have an explicit NCI-CTCAE grading criterion, observed values will be categorized as 'high' (defined as $>\text{ULN}$), 'normal' (defined as \geq lower limit of normal (LLN) and \leq ULN), or 'low' (defined as $<\text{LLN}$). Then, a change from baseline will be indicated as a change in category.

Laboratory data will also be plotted to show patterns over time. Summary statistics including 25th percentile, median, and 75th percentile will be plotted for each visit by treatment group. Lines connecting individual subject results from subjects with Grade 2 or higher values will be overlaid on each figure. For lab results that are not gradable, results from subjects with values outside of 2 *ULN or 0.5*LLN will be overlaid.

All safety comparisons and associated p-values are considered exploratory, not as formal tests of hypothesis. As such, no adjustments will be made for multiple comparisons and all p-values must be interpreted cautiously.

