9.3. Adverse Events

All AEs will be classified by system organ class (SOC) and preferred term, according to a standardized thesaurus (Medical Dictionary for Regulatory Activities [MedDRA] version 23.0). The severity of AEs will be classified using the National Cancer Institute's (NCI's) Common Toxicity Criteria for Adverse Events (CTCAE) version 4.0. Each AE is entered on the electronic case report form (CRF) once at the highest severity. As such, no additional data manipulation is needed to identify events.

AEs will be collected starting at consent for Grade 2 or higher AEs related to a study-mandated procedure, treatment, or change in treatment, and will be collected starting from the first dose of study treatment through Month 18 or until 30 days after the participant prematurely terminates from the study, whichever occurs first. SAEs are collected for participants throughout the duration of their participation in the study. Treatment-emergent AEs will be identified as those with an onset date on or after the first dose of study medication. If the start of the AE in relation to the start of study medication cannot be established (e.g., the start date for the AE is missing), then the AE will be considered treatment-emergent. If an abnormal laboratory finding is reported as an AE on the first day of study drug (Day 1), these events will not be considered treatment emergent since these assessments occur prior to treatment initiation. All data tabulations will be of only treatment-emergent events while non-treatment-emergent AEs will be included in the listing of all AEs.

The frequency of AEs will be summarized by system organ class, preferred term, severity (grade), and relationship to study treatment. Relationship to study treatment, as determined by masked investigators, will be categorized as either treatment related (possibly, probably, or definitely related to study medication) or unrelated (unlikely related or unrelated). Similar analyses will be performed for SAEs. To account for differential duration of study participation among participants, the summaries will also include the event rate (i.e., number of events per person-time) in addition to the number and percent of events and participants experiencing events.

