For the secondary safety endpoint of the proportion of participants in each arm experiencing a Grade 3 or higher AE according to the National Cancer Institute-Common Terminology Criteria for Adverse Events (NCI-CTCAE) system, the proportion of participants experiencing at least one event in each treatment group will be reported and the treatment groups compared based on Fisher's Exact Test.

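### AE event rates have no defined person-time, and the Grade 3+ endpoint combines an 18-month window (non-serious) with a 36-month window (serious)

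*SAP*

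**What the plan says.** **Collection windows.** SAP 9.3 says that AEs "will be collected starting from the first dose of study treatment through Month 18 or until 30 days after the participant prematurely terminates", whichever comes first. The footnote to Protocol Table 6.2 confirms the limit: "Non-serious adverse events will not be collected after Month 18". SAEs follow a different rule. Protocol 7.3.2 states: "Serious adverse events will be collected throughout the duration of the subject’s participation in the study". SAP 9.3 agrees. Protocol 3.1 plans 36 months of participation.

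**Event rate.** SAP 9.3 introduces the rate with "To account for differential duration of study participation among participants, the summaries will also include the event rate (i.e., number of events per person-time". Protocol 8.3.2 uses nearly the same sentence, and SAP 9.4 repeats it for SAEs. None of the three defines person-time. SAP 9.2 defines duration of exposure from first to last dose but does not tie it to the AE rate.

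**Treatment-emergent and Grade 3+.** SAP 9.3 treats an event as treatment-emergent if its onset is on or after the first dose, sets no end date, and bases all tabulations on such events. For the Grade 3 or higher endpoint, "the proportion of participants experiencing at least one event in each treatment group will be reported", with a Fisher's exact comparison. Neither SAP 9.3 nor Protocol 3.3.2 gives this endpoint a time window.

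**The concern.** One sentence about the rate serves two kinds of event that are observed for different lengths of time. For SAEs, participation time is the right denominator. For non-serious AEs it adds up to 18 months in which no such event could be recorded. Two programmers working from this text could therefore produce non-serious rates that differ almost twofold.

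The Grade 3+ endpoint has a related problem that does not depend on person-time. A non-serious Grade 3 event at Month 20 cannot be counted, but a serious one can. Protocol 3.3.2 singles this endpoint out as being of particular interest, and the resulting percentage cannot be described as a risk over 18 months or over 36.

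At stake are the absolute AE rates and the meaning of the key safety proportion. The efficacy result is not affected.

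**Working it through.** The documents give no AE rate, AE count or AE person-time, so there is no stated figure to reproduce. The person-time figures in the interim plan (SAP Appendix 14.1, Table 3) are consistent: 144 × 3 = 432 person-years, 366.5/432 = 0.848 and 405.4/432 = 0.938.

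**Inputs**
- AE window: 1.5 years (SAP 9.3; Month 18 has target day 548 in SAP Table 4).
- Participation: 3.0 years (Protocol 3.1; Month 36 has target day 1096).
- Loss: 20% in each arm (interim plan, Appendix 8.1), taken here as exponential over 3 years.
- Early stop: recommended by the DSMB after the April 2022 interim (SAP 5.4). The dates on which follow-up ended are assumed.

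**Step 1. Dilution of the non-serious rate.** With a constant event rate, the rate over participation time divided by the rate over the collection window equals PT(1.5)/PT(3). PT(T) is mean person-time to T years. The 30 days of collection after early termination are ignored.
- Completers: 1.5/3.0 = 0.50 (548/1096 gives the same).
- 20% loss: h = −ln(0.8)/3 = 0.0744 and PT(T) = (1 − exp(−hT))/h. PT(1.5) = 1.419, PT(3) = 2.689, ratio 0.53.
- Early stop: potential follow-up on 01FEB2022 was given an assumed exponential-tilt density between 0.25 and 5.8 years, calibrated to 366.5 person-years. It then predicts 407.3 person-years at 01FEB2023, against 405.4 in the interim plan. Ending follow-up between February 2022 and February 2023, with no loss or 20% loss, gives ratios from 0.529 to 0.583.

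As an illustration, take 72 people (half of 144) who all complete and an assumed 30 non-serious events. Over the collection window the rate is 30/(72 × 1.5) = 30/108 = 0.28 per person-year. Over participation it is 30/(72 × 3) = 30/216 = 0.14.

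**Step 2. All AEs combined.** If a share f of the total event rate is serious, the ratio in completers is 0.5(1 − f) + f = 0.5 + 0.5f. For f from 0 to 20% (assumed) this is 0.50 to 0.60. For SAEs alone it is 1.00.

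**Step 3. Between-arm effect.** With equal retention the dilution cancels and the rate ratio is unchanged. Suppose instead, as an assumption, that mean participation is 2.8 years in one arm and 2.4 in the other, with equal true rates.
- If the whole difference arises after Month 18, the event counts are equal and the rate ratio reads 2.8/2.4 = 1.17.
- If loss is exponential with the same means, person-time to Month 18 is 1.449 and 1.339 years. The ratio is (1.339/2.4)/(1.449/2.8) = 1.08. These means imply three-year losses of about 13% and 37%.

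**Step 4. Grade 3+ proportion.** With assumed constant hazards a (non-serious) and b (serious) per year, in completers:

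| a, b | Both to Month 18: 1 − exp(−1.5(a + b)) | As written: 1 − exp(−(1.5a + 3b)) | Both to Month 36: 1 − exp(−3(a + b)) |
|---|---|---|---|
| 0.05, 0.03 | 11.3% | 15.2% | 21.3% |
| 0.03, 0.03 | 8.6% | 12.6% | 16.5% |
| 0.08, 0.02 | 13.9% | 16.5% | 25.9% |

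In each row the figure as written falls between the two single-window figures.

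**The case against.** The strongest reply is that the SAP never says person-time runs to Month 36. Participation appears only in the clause giving the rate's purpose, and the Month 18 limit stands earlier in the same section. A programmer could stop AE person-time at Month 18 without departing from the text. This stands. A reader might infer that the plan prescribes a 36-month denominator and that rates will be halved, but the documents leave the denominator open. Halving follows only if participation time is used, and then only for non-serious events in completers.

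A reader might also infer that the comparison between arms is biased. The documents plan 20% loss in each arm, and under equal retention the ratio is unchanged. The 1.17 in Step 3 needs all the differential loss to fall after Month 18.

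For Grade 3+ events, both arms share the same collection rules, so the mixed window does not by itself bias the Fisher comparison. Nor can late serious events be dismissed as unrelated to a 12-month course: Protocol 1.4.2.1 describes retinopathy reported years after antimalarial treatment stopped, and a case of vision loss beginning a year after hydroxychloroquine was discontinued. Replacing the endpoint with a Month 18 version could remove the late toxicity the protocol describes. It would also alter a protocol-defined endpoint in a trial where, by SAP 5.4, assignments are unmasked before database lock.

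Finally, counts and percentages are reported beside the rate, SAEs have their own summary, and Protocol 8.3.2 calls all safety comparisons exploratory. These points limit the consequence. They do not supply the missing definition or give the Grade 3+ proportion a follow-up period.

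**Conclusion.** The concern holds in a limited form. Person-time is undefined, and the only basis offered does not match the period over which non-serious AEs are collected. If participation time is used, non-serious rates are 0.50 of their collection-window value in 36-month completers, 0.53 with 20% exponential loss, and about 0.53 to 0.58 with the early stop. These figures assume constant event rates, and the last range also rests on assumed stopping dates and an assumed accrual curve. SAE rates, counts and percentages do not change, and rate ratios are largely preserved if retention after Month 18 is similar.

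The mixed window in the Grade 3+ endpoint follows directly from the text and needs no assumption about person-time. Its size depends on hazards the documents do not give. The documents do not support the stronger conclusions that the plan fixes a 36-month denominator, that the arms are compared unfairly, or that late SAEs should be dropped.

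**What to change.** - **SAP 9.3:** define AE person-time as running from first dose to the earliest of Month 18, 30 days after early termination, or study end. For all-AE rates, count only onsets within that window.
- **SAP 9.4:** define SAE person-time as running to the end of participation.
- **Grade 3+ endpoint:** keep the protocol-defined comparison. Add the same comparison restricted to onset from first dose to Month 18, and tabulate later SAEs by arm.
- **SAP section 12:** record the added comparison.

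No new data are needed. The cost is a few sentences and one extra table.

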9.4. Deaths, Serious Adverse Events, and Other Significant Adverse Events

The frequency of SAEs will be summarized by system organ class, preferred term, severity (grade), and relationship to study treatment. Relationship to study treatment, as determined by masked investigators, will be categorized as either treatment related (possibly, probably, or definitely related to study medication) or unrelated (unlikely related or unrelated). To account for differential duration of study participation among participants, the summaries will also include the event rate (i.e., number of events per person-time) in addition to the number and percent of events and participants experiencing events.

9.5. Clinical Laboratory Evaluation

For these analyses, clinical laboratory measurements include serum chemistry and hematology, and exclude autoantibody and CRP levels, which will be evaluated in the Secondary Objectives. Laboratory results will be reported from a central lab. However, sites can additionally report unscheduled results performed locally in the EDC. Local results will be converted to standardized units where possible. Changes in laboratory parameters that represent increases NCI-CTCAE severity grade over time are captured as AEs and summarized as described in Section 9.3.

Laboratory parameters will be summarized both overall and by treatment group using appropriate descriptive statistics. For each lab parameter, the number and percent of participants that have an increase, decrease, or no change from Baseline to Week 24 and Week 52 will be displayed for each treatment group and pooled across treatment arms. For parameters with an explicit NCI-CTCAE grading criterion, change from baseline will be indicated by a change in grade. For parameters that do not have an explicit NCI-CTCAE grading criterion, observed values will be categorized as 'high' (defined as $>\text{ULN}$), 'normal' (defined as \geq lower limit of normal (LLN) and \leq ULN), or 'low' (defined as $<\text{LLN}$). Then, a change from baseline will be indicated as a change in category.

Laboratory data will also be plotted to show patterns over time. Summary statistics including 25th percentile, median, and 75th percentile will be plotted for each visit by treatment group. Lines connecting individual participant results from participants with Grade 2 or higher values will be overlaid on each figure. For lab results that are not gradable, results from participants with values outside of $2 * \text{ULN}$ or $0.5 * \text{LLN}$ will be overlaid.

10. OTHER ANALYSES

Other analyses that may be considered post-hoc include:

- For participants who developed CL-RA during the study, we may examine characteristics and features of the diagnosis by treatment group. The features of diagnosis may include (but are not limited to) disease activity measures (e.g. DAS28CP), x-ray findings (e.g. presence of erosions and Sharp's scores) and persistence of tender and swollen joints post-diagnosis.
- For participants who developed CL-RA during the study, we may examine the severity of the CL-RA symptoms at the time of diagnosis by treatment group. Severity can be measured using DAS28-CRP, CDAI, RAPID-3, and PROMIS scores at the time of diagnosis.
- We may examine relationships between dietary intake and/or other environmental exposures and development of the CL-RA.

Additional mechanistic analyses may be performed, and the details of those analyses will be specified in separate statistical analysis plans.

11. INTERIM ANALYSES AND DATA MONITORING

11.1. Interim Analysis of the Primary Objective

The details for the planned interim analyses are provided in the ARA08 Interim Statistical Analysis Plan, which was finalized as version 1.0 on December 17, 2021. The ARA08 Interim Statistical Analysis Plan is included as Appendix 14.1.

The first interim analysis was conducted in April 2022, and the results of the interim analysis, “Interim Analysis for the April 2022 DSMB”, were included as an appendix in the closed report to the Data and Safety Monitoring Board on April 6, 2022 as part of the regularly scheduled review of the ARA08 study.

12. CHANGES TO THE ANALYSES PLANNED IN THE PROTOCOL

- Protocol section 8.3.1.2 states "All efficacy analyses will be repeated using the PP population." We have modified this plan for secondary efficacy analyses. PP analyses maybe conducted at the discretion of the study team if warranted by results of the mITT analyses.
- Protocol section 8.3.1.1 states "The primary analysis ignores the possible impact of within-family correlation. The propensity to progress to RA could be more similar within families than between families or across individuals in the population, in which case observations in this study would not be independent. Due to operational difficulties in linking family members, we expect to have incomplete information on familial clustering, so we will not be able to account for this potential correlation in the primary analysis. Because families tend to be small and not all family members will be eligible or willing to participate, we anticipate the impact of clustering to be small. We will, however, perform sensitivity analyses to assess the potential impact of clustering. We are asking participants if they have FDRs who are participating. If the proportion who answer affirmative is small, the impact of clustering is likely to be minimal. In addition, participants have the option of linking their study records with those of their relatives. If family clusters are identified through this process, we can estimate the treatment effect from a marginal Cox model for clustered data using the method of Lee, Wei, and Amato [178] and compare these to estimates derived from the usual Cox model assuming independent observations. We could also compare estimates for the risk of developing RA derived from logistic regression models fit using generalized estimating equations under difference assumptions about the within-family correlation structure; independent versus exchangeable [179]."

Upon review of the data collected in ARA08 regarding members of the same family participating in ARA08, it was discovered that no participants reported having an FDR who was also participating in the study. As a result, sensitivity analyses to assess the impact of family clustering will not be performed.

ISAP	Interim Statistical Analysis Plan
IBW	Ideal body weight
ITT	Intent-to-Treat Population
KM	Kaplan-Meier
Max	Maximum
Min	Minimum
mITT	Modified Intent-to-Treat Population
PP	Per Protocol Population
RA	Rheumatoid Arthritis
SAP	Statistical Analysis Plan
SD	Standard deviation
SP	Safety Population

1. PURPOSE OF THE ANALYSES

We will conduct one or possibly two interim analyses to stop the study early for overwhelming evidence of efficacy or futility. Results from the first interim analyses will supplement the usual safety and study conduct information presented to the Data and Safety Monitoring Board (DSMB) at the spring 2022 meeting. Results of these analyses are not binding. The DSMB will provide recommendations on study continuation to DAIT. In the event of a recommendation to stop the study, DAIT will convene an unmasked panel to consider the recommendations.

The purpose of this interim statistical analysis plan (ISAP) is to describe the planned interim efficacy and futility analyses and associated data displays to be included in the interim analysis reports for Protocol ARA08. This document provides details on the analysis population, derivation of variables, plans for handling of missing data, and statistical methods to be used in these analyses.

This ISAP is based on ICH guidelines E3 and E9 (Statistical Principles for Clinical Trials).

